4.2 Anticipated Number of Research Subjects

Enrollment into the investigation will be defined as providing informed consent for study participation per IRB policies.

Twenty-one (21) subjects will be enrolled and all are anticipated to complete the study.

4.3 Inclusion Criteria

- 1. Moderate to severe knee pain (VAS > 50 mm), and
- 2. Pain refractory to at least 3 months* of conservative therapies (antiinflammatory drugs, or physical therapy, or muscle strengthening, or intraarticular injections), and
- 3. Kellgren-Lawrence grade 1, 2 or 3 on radiograph of the knee.
- 4. Age > 40 years.

*3 months was chosen because this time interval is thought adequate for knee pain to be considered refractory to conservative care.

4.4 Exclusion Criteria

- 1. Current local infection, or
- 2. Life expectancy less than 6 months, or
- 3. Known advanced atherosclerosis, or
- 4. Rheumatoid or infectious arthritis, or
- 5. Prior knee replacement surgery, or
- 6. Uncorrectable coagulopathy including INR > 2.5 or platelets < 30,000, or
- 7. Iodine allergy resulting in anaphylaxis, or
- 8. Renal dysfunction as defined by serum creatinine >1.6 dl/mg or eGFR <60 obtained within the past 30 days.

4.5 Subject Recruitment and Screening

Subjects will be recruited from orthopedic and interventional radiology clinics in

the Northern Virginia Area or the Vascular Interventional Radiology Clinic at UNC-Chapel Hill.

4.6 Early Withdrawal of Subjects

- 4.7.1 Criteria for Removal from Study
 - Subjects will be withdrawn from the study if
 - a. a major complication occurs that prevents completion of GAE or the ability to complete the follow up visits, or
 - b. at any point at their discretion.

4.7.2 Follow-up for Withdrawn Subjects

If a subject withdraws from the study, any recorded data will still be included in the analysis. Subjects will only be replaced if they withdrew prior to undergoing GAE.

5 Study Treatment or Diagnostic Product Procedures 5.1 Description

Subjects will not initiate any new pain therapy or escalate current therapy for 1 month prior to GAE. They will be given an intravenous dose of antibiotics on the day of the procedure and continue with oral antibiotics for seven days after the procedure. The subjects will be given the choice of receiving intravenous anxiolytic and analgesic medication during procedure or proceeding with local anesthetic only.

Arterial access site will be prepped and draped using sterile technique. Ultrasound-guided access may be used and arterial access will be obtained. An intra-arterial sheath will be placed. Through this sheath a guiding catheter will be used to perform lower extremity angiography on the targeted side. Using the guiding catheter and a microcatheter, the geniculate arteries supplying hypervascular synovial tissue in the region of the knee joint will be catheterized. This will allow the operators to know exactly what tissues will be receiving the Gel-Bead embolization spheres; OptiSphere embolization spheres. Gel-Bead embolization spheres; OptiSphere embolization spheres ranging from 100-500 microns*, selected at the operator's discretion based upon size of target vessels, will then be injected under fluoroscopic guidance to prevent reflux and non-target embolization. Injection will continue until an end point of at least 'near stasis' (slowed antegrade flow of contrast). Multiple geniculate arteries may be embolized until neovascularity is no longer seen. A repeat lower extremity angiogram will then be performed to evaluate for success of embolization and to exclude complication. The catheter and sheath will then be removed and hemostasis will be achieved with manual compression or a vascular closure device. The subject subsequently will be discharged home the same day (<23hours) unless a complication arises that requires inpatient admission for management of the complication. Subjects may be discharged on pain medications as needed for post-operative care (<14 days).

*The range in size of particles will allow the operators to discern the safest, most effective size for the vessels targeted. For example, if the catheter can be

advanced all the way in to the branch supplying only the synovium, smaller particles can be safely used to induce ischemia in the target tissue. If the catheter cannot be advanced due to tortuous or small caliber vessels, a larger sized particle may be selected. This will allow for proximal embolization without distal penetration into the cutaneous branches, thereby allowing continued blood flow to the skin through collateral pathways (**Fig 1-2**). This concept is utilized routinely within embolization procedures are commonly performed.

[figure not shown]

Fig 1. Geniculate artery angiogram after total knee arthroplasty demonstrating "contrast blush" denoting hypervascular synovium (bold arrow). Separate arterial branches are seen supplying the joint tissue (arrow) and skin (dotted arrow). At this point an attempt would be made to place a microcatheter in the synovial branch. If impossible due to the size of the target vessel, embolization would be performed from this catheter location using larger particles to preserve distal collateral supply to the skin.

[figure not shown]

Fig 2. Lateral angiogram of the knee with selective catheterization of the synovial branch of the geniculate artery. In this circumstance, smaller sized embolic particles would be appropriate because cutaneous branches are not seen.

It is anticipated that less than 5 milliliters of Gel-Bead embolization spheres; OptiSphere embolization spheres will be required for embolization. Gel-Bead embolization spheres; OptiSphere embolization spheres currently have FDA approval for embolization of hypervascular tumors.

5.2 Method for Assigning Subject to Treatment Groups

Subjects who meet all criteria for study entry and have signed written informed consent will be randomized in a 2:1 allocation of treatment (geniculate artery embolization) versus placebo (angiogram). Patients will be blinded to the study procedure. Each patient will be told at the time of recruitment that they may be

randomly assigned to GAE or sham. If after 1 month if they have not had symptom improvement, their assigned procedure would be revealed only if they had undergone a sham procedure. They will then be allowed to proceed with embolization in Arm C if they elect to proceed. This second procedure should be shorter than a complete angiogram and embolization, as the detailed angiogram will not need to be repeated. See table 1 (study schema). A 2:1 ratio was selected so that patients would be more likely to enroll in the study.

5.3 Subject Compliance Monitoring

Study coordinators and physicians will inquire of the subjects to determine if they have escalated any current or initiated any new conservative therapies during the follow-up period.

5.4 Prior and Concomitant Therapy

The subjects will be required to have been on conservative therapy for OA for at least three months prior to undergoing GAE. They will be allowed to continue previously initiated therapies throughout the study period, but if new or escalated therapies are required past the post-operative period (14 days), the treatment will be considered a failure.

5.5 Blinding of Study

Following randomization, efforts will be made to blind the subject to the study procedure. Patients will not be informed to their treatment or placebo arm. As the procedures of a diagnostic angiogram and embolization are similar (femoral artery access, angiogram, post-operative care), the subject will inherently not know if he/she received the treatment or placebo. The post-operative staff caring for the patient will not be informed as to the treatment the patient received. Datasets for each arm will be presented for analysis by statistician labeled as treatment arm (i.e. A, B or C).

5.6 Receiving, Storage, Dispensing and Return

5.6.1 Receipt of Investigational Device Supplies

Medtronic will provide, at no charge, up to six (6) boxes (5 vials/box) of Gel-Bead Microspheres for the Study ("Devices"). Gel-Bead embolization spheres; OptiSphere embolization spheres will be stored within the Interventional Radiology Department in a separate area. Embolic devices will be labeled 'for investigational use only' and will be reserved for use in the clinical trial.

5.6.2 Storage

Gel-Bead embolization spheres; OptiSphere embolization spheres must be stored in a cool, dark, dry place in their original packing.

5.6.3 Dispensing

No study specific dispensing techniques will be used.

5.6.4 Return or Destruction of Investigational Device

The Institution and Sponsor-Investigator shall, return any such Product to

Company promptly if requested by the Company upon the completion or termination of the Study for which such Product was being utilized, or promptly dispose of or destroy, as the Company may reasonably direct, all of its remaining stocks of Product. All Devices supplied by Medtronic to Institution for the Study shall be used by Institution only as specified in the Protocol and the Clinical Trial Agreement. No other use of the Devices is authorized.

Disposable syringes, which spherical particulate is stored in, will be discarded as medical waste and packaging will be kept in a secure location until the study is completed. Packages will be disposed of upon completion of the study.

Lot numbers of the device used will be recorded in the CRFs for the study procedure.

6 Study Procedures

6.1 Screening Visit (Visit 1)

Potential enrollees will first be identified and will undergo a standard knee OA work-up to include history and physical exam with emphasis on specific site of knee tenderness. The Western Ontario and McMaster University Osteoarthritis Index (WOMAC) questionnaire will be administered to assess difficulty as a result of pain, stiffness and overall decreased function secondary to knee pain in the past week.

Current pain will also be assessed using a visual analog scale (VAS). A knee radiograph will be obtained and evaluated using the Kellgren-Lawrence grading scale. A baseline knee MRI will also be acquired to evaluate for concomitant pathology as part of routine orthopedic evaluation. If the patient previously had an MRI for clinical care that can be obtained from his/her medical record and used for the purposes of this study.

If a patient qualifies to be a subject in the study based on the inclusion and exclusion criteria listed in section 4.3 and 4.4, the local study coordinator, investigator or designee will provide the candidate with a copy of the approved informed consent. Written informed consent will be obtained if appropriate. If the patient wishes to take more time to review the study before enrolling, he/she may complete the consent process at the beginning of the next visit, prior to the study GAE procedure. Those candidates who are disqualified from study entry will be logged into the Screening Log with a reason for no study entry. A copy of the consent will be provided to the subject and the original filed in the study files.

Patients will be randomized at this point according to the schema created prior to the commencement of the study.

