6.2 Visit 2 GAE or Sham Procedure

GAE or sham procedure will be performed as described in part 5.1 above within 4 weeks of Visit 1. Subjects will be given a pager number to reach a physician (24 hours a day) to report any adverse symptoms and receive medical advice. The

sham procedure patients will be provided with the same information and followup instructions.

If a patient does not undergo the procedure within the specified visit window, then the WOMAC and VAS questionnaires should be repeated prior to the procedure.

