10.3 Case Report Forms

The study case report form (CRF) is the primary data collection instrument for the study. All data requested on the CRF must be recorded. All missing data must be explained. If a space on the CRF is left blank because the procedure was not done or the question was not asked, write "N/D". If the item is not applicable to the individual case, write "N/A". All entries should be printed legibly in black ink. If any entry error has been made, to correct such an error, draw a single straight line through the incorrect entry and enter the correct data above it. All such changes must be initialed and dated. DO NOT ERASE OR WHITE OUT ERRORS. For clarification of illegible or uncertain entries, print the clarification above the item, then initial and date it.

Copies of completed CRFs with subject IDs will be scanned and sent to the lead study coordinator at UNC for verification through the study database. Data should be entered in the study database within 5 business days to ensure timely entry.

The coordinator at each site will complete the first CRF together with one of the Co-PIs to verify that it is completed correctly. Then, we will verify a randomly selected 25% of all source docs at the conclusion of data collection. Randomization will occur on a visit level and not per patient. The randomization for this verification will be generated using a random number generator in Excel. A concealed randomization look-up table will be generated in collaboration with the biostatistician and installed in the REDCap database. Assignments remain concealed to the staff until the moment the participant is enrolled online in the REDCap database.

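### Randomising at Visit 1 can leave enrolling staff aware of the allocation for up to four weeks or longer before the procedure, so randomised subjects can be lost selectively and replaced

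*Combined protocol and SAP*

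**What the plan says.** **Timing of randomisation.** Section 6.1, which describes Visit 1, ends: "Patients will be randomized at this point according to the schema created prior to the commencement of the study". The paragraph before it deals with consent and says that a patient who wants more time may defer: "he/she may complete the consent process at the beginning of the next visit, prior to the study GAE procedure".

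**Condition for randomisation.** Section 5.2 is stricter: "Subjects who meet all criteria for study entry and have signed written informed consent will be randomized in a 2:1 allocation". Section 4.2 adds: "Enrollment into the investigation will be defined as providing informed consent for study participation per IRB policies".

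**Concealment and blinding.** Section 10.3 states: "Assignments remain concealed to the staff until the moment the participant is enrolled online in the REDCap database". After that point, sections 3.1 and 5.5 blind the subjects and the nursing or post-operative staff. No section blinds coordinators, investigators or operators between enrolment and the procedure.

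**Gap to the procedure.** Section 6.2 states: "GAE or sham procedure will be performed as described in part 5.1 above within 4 weeks of Visit 1". If that window is missed, the subject stays in the study and WOMAC and VAS are repeated before the procedure.

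**Subjects lost in the gap.** Section 4.7.2 replaces those who withdraw before GAE, and also says that data recorded on withdrawn subjects remain in the analysis. Section 8.3 makes receipt of GAE or sham a condition of being evaluable. No analysis set of all randomised subjects is defined.

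**The concern.** Concealment should last until a subject is committed to the study treatment. Here it can end weeks earlier for anyone who consents at Visit 1. In the interval, staff who may know the arm arrange the procedure date, answer questions and take calls from subjects who are having doubts. If their conduct differs by arm, even unintentionally, the subjects who reach the procedure are no longer a random split of those allocated.

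The replacement rule and the treated-only evaluable set compound this. A subject lost in the gap can be exchanged for another and left out of the comparison, while the final count still reads 21. The loss would then not show in the sample size, and the plan does not ask for such losses to be reported by arm. With about 7 sham subjects, each is about one seventh (14%) of the control mean.

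**Working it through.** **1. Who has a gap, and how long.**

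- *Consent signed at Visit 1.* The condition in 5.2 is met, the subject is enrolled under 4.2, concealment ends under 10.3 and 6.1 randomises. The procedure follows "within 4 weeks of Visit 1", so the gap is up to 28 days. It has no stated upper limit if the window is missed.
- *Consent deferred to Visit 2.* Read alone, 6.1 could randomise at Visit 1 before signature. Sections 5.2, 4.2 with 10.3, and 12 (written consent before any study procedure) all point to assignment only after signature. On that reading the gap falls within one visit.

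The exposure therefore rests on the Visit 1 consenters. The deferred case is a conflict of wording.

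**2. What happens to a subject lost in the gap.** Under 4.7.2 the subject is replaced and any recorded data (in practice the baseline scores) are kept. Under 8.3 the subject is not evaluable. The two sections disagree. Even if 4.7.2 governs, a subject with only a baseline record informs the starting level in the 8.2 random coefficient model and carries no direct information on the 6-month contrast. Including such subjects helps only as far as missing-at-random holds.

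**3. The plan's own figures.** Inputs are 21 subjects at 2:1 (3.1), so 14 GAE and 7 sham, and one-sided alpha 0.05 (8.2; 8.1 gives no alpha). Means, SDs and effects come from 8.1. The check uses a two-sample t-test with 19 df and noncentrality d / √(1/14 + 1/7), where the root is 0.463.

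| | Difference | d | Noncentrality | Power found | Power stated |
|---|---|---|---|---|---|
| WOMAC | 0.16 × 12.2 = 1.952 | 1.952 / 1.9 = 1.027 | 2.22 | 69.0% | 69.1% |
| VAS | 0.15 × 72 = 10.8 mm | 10.8 / 13.3 = 0.812 | 1.75 | 51.9% | 51.7% |

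This confirms a planned sham arm of 7 and a VAS target of 10.8 mm.

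**4. Illustrative size of the bias.** Suppose k of 7 sham subjects are lost and replaced by subjects whose VAS differs on average by δ. The sham mean then moves by k × δ / 7. Neither k nor δ is in the documents; both are assumed.

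| k | δ (mm) | Shift (mm) | Share of 10.8 mm |
|---|---|---|---|
| 1 | 10 | 1.4 | 13% |
| 1 | 15 | 2.1 | 20% |
| 2 | 10 | 2.9 | 26% |
| 2 | 15 | 4.3 | 40% |

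If the GAE arm is unaffected, the treatment difference moves by the same amount, in a direction that cannot be known in advance.

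**5. Replacement protects power, not comparability.** Without replacement, losing 1 sham subject (14 v 6) gives 64.8% for WOMAC and 48.3% for VAS; losing 2 (14 v 5) gives 59.8% and 44.1%. Replacement restores the planned figures but leaves the shift in step 4 untouched.

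**The case against.** The strongest reply is that the safeguards are better than section 6.1 alone suggests.

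- *Consent.* A reader might infer that some subjects are randomised before they consent, and that a known allocation could influence the consent discussion. The documents do not support this as the plan's practice. Section 5.2 requires signature first, 4.2 with 10.3 ties release of the assignment to consent, and section 12 requires written consent before any study procedure. What stands is an inconsistency in 6.1.
- *Analysis.* A reader might also infer that lost subjects are certainly dropped and that no analysis could help. Section 4.7.2 says the opposite about recorded data, and the 8.2 model accepts incomplete records under missing-at-random. What stands is the conflict between 4.7.2 and 8.3, and the limited information in a baseline-only record.
- *Who knows the arm.* Section 10.3 says when concealment ends, not which staff then see the assignment. Visibility to enrolling and research staff is an inference, though a natural one, since nothing later restores concealment. Nursing and post-operative staff are to be blinded, and operators must know the arm at the procedure in any case.
- *Subject blinding.* Subjects do not know their arm, so selective loss would need staff action or accidental disclosure. The repeat baseline applies only when the window is missed and is answered by a blinded subject. Both points lower the risk without removing it.
- *Likelihood.* Section 4.2 expects all 21 to complete, and nothing in the documents shows that selective loss will occur. This is correct, and it is why the shift in VAS is only an illustration.

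**Conclusion.** The point holds for subjects who consent at Visit 1. Their allocation may be known to enrolling staff for up to 4 weeks, or longer, before the procedure. A subject lost in that time is replaced and, under 8.3, is not evaluable. The plan thus allows selective post-randomisation loss that would not show in the final count.

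The size is uncertain. On the assumed inputs (1 or 2 of 7 sham subjects, 10 to 15 mm apart) the sham VAS mean moves by 1.4 to 4.3 mm, or 13% to 40% of the 10.8 mm target. The arithmetic is exact, but the inputs are assumptions and the direction is unknown. The conclusion also rests on reading 10.3 to mean that enrolling staff can see the assignment once the subject is enrolled. It does not rest on anyone being randomised without consent.

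The change is worth making because it is cheap: the plan gives no reason for releasing the assignment at Visit 1, and it is needed only at the procedure.

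**What to change.** 1. **Release the allocation on procedure day.** Open the REDCap assignment only after signed consent, confirmed eligibility and completed (or repeated) baseline WOMAC and VAS, and as close to the start of the procedure as possible. Releasing it after the diagnostic angiogram common to both arms would nearly close the gap. It must then not be disclosed to the subject, who may be awake because 5.1 allows local anaesthetic only, or to nursing staff who are to be blinded.
2. **Reconcile 6.1 with 5.2.** State that signed consent always precedes randomisation, including for patients who defer consent to Visit 2.
3. **Reconcile 4.7.2 with 8.3.** Define the primary analysis set as all randomised subjects. Clarify the replacement rule, which refers only to GAE and leaves its application to sham subjects unclear. With late release it should rarely be needed.
4. **Report losses** between randomisation and procedure by arm, with reasons.

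The cost is protocol wording and some logistics: someone must open REDCap on the day, the device must be on hand for every case, and in-suite release needs care to protect blinding. Planned sample size and power do not change.

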6.2 Visit 2 GAE or Sham Procedure

GAE or sham procedure will be performed as described in part 5.1 above within 4 weeks of Visit 1. Subjects will be given a pager number to reach a physician (24 hours a day) to report any adverse symptoms and receive medical advice. The

sham procedure patients will be provided with the same information and followup instructions.

If a patient does not undergo the procedure within the specified visit window, then the WOMAC and VAS questionnaires should be repeated prior to the procedure.

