7.2 Effectiveness Assessments

Technical success will be defined as devascularization of hypervascular synovium at the affected knee. This will be determined during the procedure. Clinical success will be defined as a 16% reduction of the baseline global WOMAC score at 1 or 6 month follow-up (primary outcome) and a 15% reduction of the baseline pain VAS score at 6 or 1 month follow-up (primary outcome).

8 Statistical Plan

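### The screening VAS that admits a subject also serves as baseline, so within-arm VAS reductions and responder rates contain some regression to the mean

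*Combined protocol and SAP*

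**What the plan says.** - Section 4.3 makes pain intensity an entry test: "Moderate to severe knee pain (VAS > 50 mm), and".
- Section 6.1 (Visit 1) schedules the scores. For VAS: "Current pain will also be assessed using a visual analog scale (VAS"). For WOMAC, the wording is: "questionnaire will be administered to assess difficulty as a result of pain, stiffness and overall decreased function secondary to knee pain in the past week".
- Section 6.1 then randomizes: "Patients will be randomized at this point according to the schema created prior to the commencement of the study". Under section 10.3 the assignment is hidden from staff only until the participant is enrolled in REDCap.
- Section 6.2 sets the gap: "GAE or sham procedure will be performed as described in part 5.1 above within 4 weeks of Visit 1". If the procedure falls outside that window, "then the WOMAC and VAS questionnaires should be repeated prior to the procedure". It does not say whether the repeated score replaces the first.
- Section 5.1 sets the therapy rule: "Subjects will not initiate any new pain therapy or escalate current therapy for 1 month prior to GAE".
- Section 7.2 measures success against baseline: "Clinical success will be defined as a 16% reduction of the baseline global WOMAC score", with 15% for VAS. Section 3.2 uses the same percentages.
- Section 8.2 lists baseline among the data collection points without naming the visit. It also weighs a percentage predicted mean difference without naming its reference value.

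**The concern.** When one noisy rating both selects a subject and serves as the starting point, the next rating is lower on average even if nothing has changed. Subjects who pass a threshold on a bad day carry that day into their baseline. Here the rating is a single measure of current pain, and no second pre-procedure score is scheduled for anyone treated on time.

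What is at stake is the within-arm reading: mean VAS change, the 15% responder rate in each arm, and any statement that a given share of GAE subjects reached clinical success. The reference is also uneven. A subject treated on day 28 has an entry-selected score four weeks old, while one treated on day 29 has a fresh score as well, with no rule on which counts.

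The therapy rule is a smaller matter. It runs back from the procedure, so for a late procedure it says little about the time before the baseline score.

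**Working it through.** **Inputs from the documents.** VAS entry above 50 mm (4.3). Expected baseline VAS mean 72, range 54 to 100, SD 13.3 (8.1). N = 21 at 2:1, so 14 and 7 (3.1). Procedure 0 to 28 days after Visit 1 (6.2). One-month visit at 30 ± 7 days (6.5). VAS success threshold 15%, which is 0.15 × 72 = 10.8 mm.

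**Assumed, because the documents do not give them.** Mean and SD of VAS among everyone screened, and the test-retest correlation r.

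**The plan's own figures reproduce.**
- SD from mean and range: √{[(54 − 2×72 + 100)²/4 + (100 − 54)²]/12} = √[(25 + 2116)/12] = 13.36, against 13.3 stated.
- VAS power: d = 10.8/13.3 = 0.812, 14 v 7, one-sided 0.05, noncentral t: 51.9%, against 51.7% stated.
- WOMAC power: d = 0.16 × 12.2/1.9 = 1.027: 68.9%, against 69.1% stated.

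This point does not change these figures.

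**Regression to the mean.** Take screened VAS as normal with mean μ and SD σ, keep first ratings above 50, and assume no treatment effect. With a = (50 − μ)/σ and λ = φ(a)/[1 − Φ(a)], the entrants' mean is μ + σλ and the expected later fall is (1 − r)σλ.
- *Entrants like the protocol's.* Solving for an entrant mean of 72 and SD of 13.3 gives μ = 67.7 and σ = 16.5. Then σλ = 4.30, and the fall is 0.2 × 4.30 = 0.86 mm at r = 0.8 and 0.5 × 4.30 = 2.15 mm at r = 0.5.
- *Wide case.* μ = 55, σ = 20: a = −0.25, λ = 0.646, σλ = 12.9. The fall is 2.6 mm at r = 0.8 and 6.5 mm at r = 0.5.

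Responder rates come from simulation (2,000,000 draws; true score plus independent error; one follow-up visit). Each cell gives the result without, then with, first ratings above 100 discarded.

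| Case | r | Mean fall, mm | Fall, % | 15% responders, screening baseline | 15% responders, fresh baseline | Fresh score ≤ 50 mm |
|---|---|---|---|---|---|---|
| Protocol-like | 0.8 | 0.9 / 0.7 | 1.2 / 0.9 | 15.8 / 15.7% | 14.0 / 14.2% | 6.6 / 6.8% |
| Protocol-like | 0.5 | 2.1 / 1.7 | 3.0 / 2.3 | 28.2 / 27.3% | 24.8 / 25.0% | 10.3 / 10.6% |
| Wide | 0.8 | 2.6 / 2.4 | 3.8 / 3.6 | 26.3 / 26.2% | 20.5 / 20.8% | 16.6 / 16.9% |
| Wide | 0.5 | 6.5 / 6.0 | 9.5 / 9.0 | 41.6 / 41.0% | 31.1 / 31.1% | 26.9 / 27.4% |

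The excess of responders is 1.5 to 3.4 points in the protocol-like case (0.3 to 0.7 of 21 subjects) and up to about 10 points in the wide case (about 2 of 21). With a fresh baseline the mean fall is zero.

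The first case is sensitive to how the 100 mm ceiling is treated. Discarding scores above 100 while still matching 72 and 13.3 needs μ = 64.7 and σ = 24.8. That gives 0.2 to 0.5 times (72 − 64.7), or 1.5 to 3.6 mm, which is still below the wide-case maximum.

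**Between arms.** Allocation does not depend on the score, so the expected fall is the same in both arms. In simulation the arms differed by about 0.1 mm or less, which is sampling error.

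**Timing.** Taking one month as 30 days, a procedure on day D makes the therapy rule start 30 − D days before Visit 1: 30 days before when D = 0, and 2 days before when D = 28. Baseline to the one-month visit can span 0 + 23 = 23 to 28 + 37 = 65 days.

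**The case against.** The strongest reply is that the trial is randomized and section 8.2 tests a difference between arms, so a shift common to both arms is harmless. That largely stands. A reader might infer that the primary test is biased, but the documents do not support this: the scores precede randomization and the shift is equal in expectation.

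Other stronger readings also fail.
- *Every reduction from baseline is inflated.* WOMAC is not an entry criterion and asks about the past week. It can regress only through its correlation with VAS, and the documents give no figure to size that.
- *Unstable therapy is built into the baseline.* For a procedure within the window, the Visit 1 score always lies inside the one-month ban, and section 4.3 requires at least 3 months of conservative therapy. What remains is that for a procedure near day 28 only about 2 days of stable therapy before the score are guaranteed.
- *Regression keeps sham subjects from crossing over.* Sections 3.1, 5.2 and 6.5 turn on whether the subject reports improvement. None ties this to change from the baseline score.

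Two further replies have force. Most of the no-effect responders in the table reflect ordinary rating variability, which a fresh baseline does not remove. And because randomization follows the Visit 1 scores, a Visit 2 baseline would be post-randomization in a single-blind trial. That is a real drawback, and the fix has to guard against it.

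**Conclusion.** The point holds for within-arm VAS results. Followed as written, the plan uses an entry-selected rating up to 4 weeks old as the reference for the 15% reduction. With entrants like those assumed in section 8.1, this adds about 0.7 to 2.1 mm (0.9 to 3.0%) to the apparent fall, against a 10.8 mm threshold, and 1.5 to 3.5 points to the responder rate. At the wide end it adds about 6 mm (9%) and 10 points.

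These sizes rest on a normal model, on r between 0.5 and 0.8, and on assumed means and SDs for the screened population.

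This is a matter of baseline definition and within-arm reporting. It gives no ground to call the primary contrast invalid. One limit: the content of the flow chart in section 6.15 is not in the text available for review, so it could not be checked for a named baseline visit. The repair is worth making because it is cheap and also settles which score counts when one is repeated.

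**What to change.** 1. In section 6.2, have every subject self-complete WOMAC and VAS at Visit 2 before the procedure. The subject must still be blinded, and preferably the assignment has not yet been released to staff. Alternatively, move randomization to after this score.
2. Name this score as the baseline for the percentage reductions in sections 3.2 and 7.2, and as time 0 in section 8.2.
3. Keep the Visit 1 VAS for eligibility only.
4. Report results against the Visit 1 score, which precedes randomization, as a sensitivity analysis.
5. State that subjects whose Visit 2 VAS is 50 mm or less stay in the analysis.

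Cost: 21 extra questionnaire sets at a visit that already takes place, using a step already written for late procedures. Response rates will look slightly lower. Some subjects will have a baseline VAS of 50 mm or less: about 7 to 11% on the protocol's own figures (1 or 2 of 21), and up to about 27% under the wide assumptions (5 or 6 of 21). Holding back the assignment until the score is taken may need a small change to the REDCap release step in section 10.3.
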